1 PROTOCOL SYNOPSIS

Name of Sponsor/Company:	Name of Product:	Name of Active Ingredient:
Trevi Therapeutics, Inc.	Nalbuphine Extended-Release	Nalbuphine HCl
	Tablets	

Title of Study:

A Phase 2, Double-Blind, Randomized, Placebo-Controlled, Two-Treatment, Two-Period Crossover Efficacy and Safety Study in Idiopathic Pulmonary Fibrosis with Nalbuphine ER Tablets for the Treatment of Cough

Study Centers:

Up to 15 centers

Publication(s):

None

Planned Study Period:	Development Phase:
May 2019 to March 2022	Phase 2

Objectives:

Primary Objectives:

- To evaluate the safety and tolerability of nalbuphine extended-release (NAL ER) tablets in the study population.
- To evaluate the effect of NAL ER tablets on the mean daytime cough frequency (coughs per hour) at Day 22 (dose 162 mg twice daily [BID]) as compared to placebo. Assessment is done using objective digital cough monitoring. Daytime is defined as the time the subject is awake in the 24 hours after the digital cough monitor is applied for use.

Secondary Objectives:

- To evaluate the effect of NAL ER tablets on the mean relative change from baseline in 24-hour (combined daytime and nighttime) cough frequency (coughs per hour) at Day 22 (dose: 162 mg BID).
- To evaluate the effect of NAL ER tablets on the mean relative change from baseline in nighttime cough frequency (coughs per hour) at, and Day 22 (dose: 162 mg BID).
- To evaluate the effect of escalating doses of NAL ER tablets on the mean change from baseline on the Evaluating Respiratory Symptoms (E-RSTM) diary cough scale (E-RS diary question number 2) by treatment at Days 9, 16, and 22.
- To evaluate the effect of escalating doses of NAL ER tablets on the mean change from baseline in the Cough Severity Numerical Rating Scale by treatment at Days 8, 15, and 21.
- To evaluate the effect of escalating doses of NAL ER tablets on the mean change from baseline in the E-RS diary breathlessness scale (E-RS diary questions 7, 8, 9, 10, and 11) by treatment at Days 9, 16, and 22.
- To evaluate the effect of escalating doses of NAL ER tablets on the mean change from baseline in the 14-item the EXAcerbation of Chronic pulmonary disease Tool (EXACT®) version 1.1 e-diary tool total score by treatment at Days 9, 16, and 22.
- To evaluate the effect of escalating doses of NAL ER tablets on the mean change from baseline in the Patient Reported Outcomes Measurement Information System (PROMIS®) Item Bank v1.0 Fatigue Short Form 7a scale by treatment at Day 21.

Name of Sponsor/Company:	Name of Product:	Name of Active Ingredient:
Trevi Therapeutics, Inc.	Nalbuphine Extended-Release	Nalbuphine HCl
	Tablets	

• To evaluate the change in the Clinical Global Impression of Change (CGI-C) over time by treatment measured at Day 21.

Methodology:

This is a double-blind, randomized, placebo-controlled, 2-treatment, 2-period crossover efficacy and safety study in IPF subjects with NAL ER tablets for the treatment of cough. The study consists of 2 treatment periods of 3 weeks, each followed by a washout period of 2 weeks.

During Treatment Period 1, eligible subjects will be randomized (1:1) to one of the following treatment arms:

- Arm 1: Active NAL ER tablets followed by crossover Placebo tablets in Treatment Period 2
- Arm 2: Placebo tablets followed by crossover NAL ER tablets in Treatment Period 2

Following 3 weeks of dosing in Treatment Period 1, subjects will complete a 2-week washout period before entering Treatment Period 2. Subjects assigned to Arm 1 will receive placebo tablets and subjects assigned to Arm 2 will receive NAL ER tablets during Treatment Period 2. A final 2-week washout period will occur at the completion of Treatment Period 2.

NAL ER Dosing

Subjects on NAL ER tablets will have the dose titrated from 27 mg once daily (QD) to 54 mg BID over a 5-day period and then maintained at 54 mg BID for approximately 4 days. Doses will be subsequently escalated and maintained at 108 mg BID over 1 week and then to 162 mg BID over 6 days.

Study Visits

Study visits will include screening to determine eligibility, and for each treatment period: visits at Day -1 for baseline assessments, at Days 8, 15, and 21 during treatment, and a follow-up at the end of the 2-week washout period. At study screening and the Day 21 visits, during each treatment period, subjects will have blood drawn for safety analysis. Pharmacokinetic (PK) analysis of nalbuphine plasma concentration will also be done at Day 21. Subjects will complete questionnaires for efficacy evaluations and undergo safety evaluations including an ECG. At the baseline and Day 21 visits, during each treatment period, site staff will place an electronic cough monitor on the subject, which will be worn until the evening of the following day in order to obtain at least a full 24-hour recording period of cough frequency. At the end of each recording session, the monitor will be removed at home by the subject prior to bedtime. Subjects will complete a daily e-diary twice per day.

Subjects who discontinue investigational product, for reasons other than withdrawal of consent, will be considered to have prematurely discontinued treatment and will be asked to complete the premature discontinuation and 2-week off-treatment safety follow-up evaluations.

Name of Sponsor/Company:	Name of Product:	Name of Active Ingredient:				
Trevi Therapeutics, Inc.	Nalbuphine Extended-Release	Nalbuphine HCl				
	Tablets					
Figure: Study Schematic						

Trantmont	Visit	Treatmont		Dose	e (mg)	
Dowind	V ISIU No	1 reatment	Ar	m 1	Ar	n 2
reriou	INO.	Day	AM	PM	AM	PM
	2	-1				
		1		27		Placebo
		2		27		Placebo
		3	27	27	Placebo	Placebo
		4	27	27	Placebo	Placebo
		5	27	54	Placebo	Placebo
		6	54	54	Placebo	Placebo
		7	54	54	Placebo	Placebo
	3	8	54	54	Placebo	Placebo
		9	54	108	Placebo	Placebo
-		10	108	108	Placebo	Placebo
Treatment		11	108	108	Placebo	Placebo
Period I		12	108	108	Placebo	Placebo
		13	108	108	Placebo	Placebo
		14	108	108	Placebo	Placebo
	4	15	108	108	Placebo	Placebo
		16	108	162	Placebo	Placebo
		17	162	162	Placebo	Placebo
		18	162	162	Placebo	Placebo
		10	162	162	Placebo	Placebo
		20	162	162	Placebo	Placebo
	5	20	162	162	Placebo	Placebo
	5	21	162	102	Placebo	1 14000
		2-We	ek Washou	t	1 lacebo	
	6	-1				
	•	1		Placebo		27
		2		Placebo		27
		3	Placebo	Placebo	27	27
		4	Placebo	Placebo	27	27
		5	Placebo	Placebo	27	54
		6	Placebo	Placebo	54	54
		7	Placebo	Placebo	54	54
	7	, 8	Placebo	Placebo	54	54
	1	0 Q	Placebo	Placebo	54	108
		10	Placebo	Placebo	108	108
Treatment		11	Placebo	Placebo	108	108
Period 2		11	Placebo	Placebo	108	108
		12	Placebo	Placebo	108	108
		13	Placebo	Placebo	108	108
	Q	14	Placebo	Placebo	108	108
	U	15	Placebo	Placebo	108	162
		10	Placebo	Placebo	162	162
		1/	Placebo	Placebo	162	162
		10	Pleast a	Pleast a	162	162
		19	Dlacaba	Placebo	162	162
	0	20	Placebo	Placebo	102	162
	У	21	Placebo Dlass1	Placebo	162	162
		22	Placebo		162	
		2-We	ek Washou	T		

Name of Sponsor/Company:	Name of Product:	Name of Active Ingredient:
Trevi Therapeutics, Inc.	Nalbuphine Extended-Release	Nalbuphine HCl
	Tablets	

Number of Subjects:

Approximately 60 subjects with diagnosed IPF will be randomized to ensure evaluable data from at least 44 subjects who complete both treatment periods.

Diagnosis and Main Criteria for Inclusion:

Inclusion Criteria

Subjects eligible for randomization to receive investigational product must meet all the following criteria:

- 1. Diagnosis of "definite" or "probable" IPF based on ATS/ERS/JRS/ALAT criteria (see *Raghu et al 2018 in Appendix 6*).
- 2. Forced vital capacity (FVC) > 40% predicted of normal.
- 3. Diffusing capacity of the lung for carbon monoxide corrected for hemoglobin $[DL_{CO}] > 25\%$ predicted of normal within the past 6 months. Subjects who have not had DLco testing may be enrolled with medical monitor approval.
- 4. Chronic cough > 8 weeks.
- 5. Adequate swallow reflex as assessed by the ability to sip 3 fluid oz (or 89 ml) of water without coughing or choking.
- 6. Daytime cough severity score \geq 4 on Cough Severity Numerical Rating Scale at screening.
- 7. Males or females age 18 years and older at the time of consent.
- 8. Females of childbearing potential must use an acceptable method of birth control (if sexually active). All females of childbearing potential must have a negative pregnancy test at the screening and baseline visits.

For the purpose of this study, all females are considered to be of childbearing potential unless they are postmenopausal (i.e., at least 1 year since last menses and age > 50 years) or surgically sterile (i.e., tubal ligation, hysterectomy, and/or bilateral oophorectomy).

Sexually active female subjects of childbearing potential are required to use 1 barrier method (e.g., condom, cervical cap, or diaphragm) of contraception in addition to 1 other method (e.g., intrauterine device in place for at least 1-month, stable hormonal contraception for at least 3 months, Essure procedure, or spermicide). For female subjects using a barrier method plus spermicide, that method must be used for at least 14 days prior to Screening.

Female subjects who are abstinent may participate in the study; however, they must be counseled on the requirement to use appropriate contraception should they become sexually active. This counseling should occur at each study visit and must be documented in source records.

- 9. Willing and able to understand and provide written informed consent.
- 10. Willing and able to comply with study requirements and restrictions.
- 11. Agree to the confidential use and storage of all data and use of all anonymized data for publication including scientific publication.

Exclusion Criteria

Subjects meeting any of the following criteria are not eligible for participation in the study:

- 1. The following conditions are excluded:
 - a) Interstitial lung disease (ILD) known to be caused by domestic and occupational environmental exposures.
 - b) Interstitial lung disease (ILD) known to be caused by connective tissue disease.
 - c) Interstitial lung disease (ILD) known to be caused by drug related toxicity.

Na Tre	me of Sponsor/Company: vi Therapeutics, Inc.	Name of Product: Nalbuphine Extended-Release Tablets	Name of Active Ingredient: Nalbuphine HCl			
2.	Currently on continuous oxyg modality Intermittent oxygen	en therapy for longer than 16 house of any duration over any give	ours at any level or delivered by any ven 24-hour period is allowed			
3.	Major psychiatric disorder, which in the opinion of the Investigator, could interfere with the assessment of anti-cough efficacy and/or safety events during the study or with the ability of the subject to cooperate with study requirements					
4.	Serum bilirubin $> 1.5 \times$ uppediagnosis of Gilbert's syndrom	er limit of normal range at scre ne.	ening unless explained by a clinical			
5.	Serum hepatic alanine amine screening.	otransferase or aspartate amino	otransferase enzymes > 100 U/L at			
6.	Estimated glomerular filtration	m rate $\leq 44 \text{ mL/min}/1.73 \text{ m}^2$ at sci	reening.			
7.	Upper or lower respiratory trac	ct infection within 4 weeks of scr	reening.			
8.	Significant medical condition successfully complete the stud	n or other factors that may in y.	terfere with the subject's ability to			
9.	History of substance abuse that the study.	t, as determined by the Investiga	tor, may interfere with the conduct of			
10.	Known intolerance or hypersen	nsitivity/drug allergy to nalbuphi	ne or vehicle components.			
11.	Pregnant or lactating female su	ıbject.				
12.	Concurrent enrollment in an o trial.	ngoing clinical trial or anticipate	ed enrollment in a concurrent clinical			
13.	Clinical diagnosis of sleep apn	ea and/or use of continuous posi	tive airway pressure (CPAP).			
14.	History of clinically significan	t head injury in past 1 month.				
15.	Clinical diagnosis of aspiration	n pneumonitis.				
16.	Clinical history of opiate with	drawal symptoms following use of	of opiates.			
17.	Documented or clinically susp	ected hypercapnia (pCO ₂ >6.0kP	Pa).			
Me	dication-related Exclusions:					
18.	Known intolerance (gastroint allergy to opioids.	estinal, central nervous system	symptoms) or hypersensitivity/drug			
19.	Exposure to any investigational	al medication, including placebo,	within 4 weeks.			
20.	Potential subjects cannot have 14 days prior to the screeni naltrexone, for the duration of	received opiates, including opiate ng period. Subjects are prohi the study.	e-containing anti-cough agents, within bited from using opioids, including			
21.	Potential subjects cannot curr Drugs that when used concom pharmacologic effects of depro CNS Depressant Class Drugs"	rently be receiving benzodiazep nitantly with opioids are known essing CNS activity (See Section).	ines or other CNS Depressant Class to have the potential to cause added 9.6.2.2 ("Benzodiazepines and Other			
22.	Potential subjects cannot neurotransmission and that wh Section 9.6.2.3 ("Serotonergic	currently be receiving med en used concomitantly with opioi Class Drugs").	dications that affect serotonergic ids can cause serotonin syndrome (See			
23.	Alcohol consumption should b of added pharmacologic effect Change of IPE related drug tree	e limited for the duration of stud s of CNS depression when used	y treatment (due to the potential cause concomitantly with opioids.			
∠4.	Change of IFF-related drug tre	aunent regimen within 8 weeks (or screening.			

Name of Sponsor/Company:	Name of Product:	Name of Active Ingredient:
Trevi Therapeutics, Inc.	Nalbuphine Extended-Release	Nalbuphine HCl
	Tablets	

Cardiac-related Exclusions:

- 25. Subjects with a history of congestive heart failure of Class 2 or higher as graded using the New York Heart Association (NYHA) classification (*Appendix 8*).
- 26. Subjects with a history of angina pectoris Grade 2 or higher as graded using the Canadian Cardiovascular Society (CCS) grading scale (*Appendix 7*).
- 27. History of ventricular tachycardia, Torsade de Pointes, or family history of sudden death.
- 28. Myocardial infarction or acute coronary syndrome within the previous 3 months, as reported by the subject.
- 29. Serum potassium below the laboratory lower limit of normal.
- 30. QTcF interval >450 ms (mean of 3 screening ECG QTcF values) if QRS <120 ms (mean of 3 screening ECG QRS values); QTcF interval >480 ms in the presence of Right Bundle Branch Block (RBBB) and/or QRS ≥ 120 ms
- 31. Heart rate < 45 bpm on any screening measurement. Subjects with a resting heart rate of < 45 bpm will have it repeated once after 5 minutes in the supine position, and if it remains < 45 bpm during the repeat, they will be considered a screen failure.
- 32. Use of a medication having a "known risk" of Torsade de Pointes (categorized as "KR" on the Credible Meds[®] website) is not permitted at entry or during the study (See *Appendix 9*). Medications associated with a potential risk of QT prolongation, but not clearly associated with

Torsade de Pointes, are permitted at study entry if the following criteria are met:

- Subject has been given medication at stable doses for a full 4 weeks prior to screening.
- Medication dose will not be increased after screening, or during the study, and it is anticipated that the subject will receive the medication for the entirety of the study.

Test Product, Dose and Mode of Administration:

NAL ER tablets, 27 mg, 54 mg, and placebo tablets BID, orally administered

Reference Therapy, Dose and Duration of Administration:

Matching placebo tablets, orally administered

Duration of Treatment:

Up to 11 weeks

Variables:

Efficacy:

Primary Efficacy Endpoint

• Mean change in daytime cough frequency (coughs per hour) from baseline as assessed by objective digital cough monitoring at Day 22 by treatment. Daytime is defined as the time the subject is awake in the 24 hours after the digital cough monitor is applied for use.

Secondary Efficacy Endpoints

- Relative change in daytime cough frequency (coughs per hour) from baseline at Day 22 (dose: 162 mg BID) by treatment.
- Relative change in 24-hour (combined daytime and nighttime) cough frequency (coughs per hour) from baseline at Day 22 (dose: 162 mg BID) by treatment.

Name of Sponsor/Company:	Name of Product:	Name of Active Ingredient:
Trevi Therapeutics, Inc.	Nalbuphine Extended-Release	Nalbuphine HCl
	Tablets	

- Relative change in nighttime cough frequency (coughs per hour) from baseline at Day 22 (dose: 162 mg BID) by treatment.
- Mean change in the E-RS diary cough subscale (E-RS diary question number 2) from baseline at Days 9, 16, and 22 by treatment.
- Mean change in the Cough Severity Numerical Rating Scale at Days 8, 15, and 21 by treatment.
- Mean change in the E-RS diary breathlessness subscale (E-RS diary questions 7, 8, 9, 10, and 11) from baseline at Days 9, 16, and 22 by treatment.
- Mean change in the 14-item EXACT v1.1 e-diary tool total score from baseline at Days 9, 16, and 22 by treatment.
- Mean change in the PROMIS Item Bank v1.0 Fatigue Short Form 7a scale from baseline at Day 21 by treatment.
- Mean change in the CGI-C over time measured at Day 21 by treatment.

Safety: Safety will be assessed based on adverse events, clinical laboratory measurements, locally reviewed and central cardiac core laboratory read ECGs, vital signs, spirometry and physical examinations.

Subjects will also complete the Subjective Opiate Withdrawal Scale (SOWS) on a daily basis via e-diary for 14 days following the last dose of investigational product, whenever that occurs and regardless of the reason (unless consent is withdrawn).

An independent Data Safety Monitoring Board (DSMB) will periodically review safety data.

Pharmacokinetics: Nalbuphine (and/or metabolites) plasma concentration will be measured at Day 21 by treatment group.

Statistical Methods:

Efficacy

The primary efficacy endpoint of percent change in daytime cough frequency (coughs per hour) will be analyzed using a mixed-effects model with sequence, treatment, and time (Day 22) as fixed effects, the baseline value as a covariate, site as a random effect, and subject as a random repeated effect. There will be no imputation for dropouts or missing data for assessments not completed at study visits. A log transformation will be applied to daytime cough frequency; in the presentation of results, log-scale fitted mean treatment group differences at Day 22 will be back-transformed to fitted ratios of geometric means.

As a sensitivity analysis, a negative binomial model will be fitted with the number of coughs at Day 22 as the outcome, with terms for sequence, treatment, and time, as well as baseline cough frequency and subject, and duration of daytime (in hours) as an offset. An autoregressive covariance structure will be assumed for study visits, and the site random effect will use an unstructured covariance matrix.

Secondary efficacy endpoints will be summarized using descriptive statistics. For continuous endpoints (e.g., change from baseline), summaries will include mean, median, standard deviation, minimum, and maximum. For discrete variables (e.g., frequency), summaries will include number of instances and percentage of total instances for that category or time period.

Safety

Name of Sponsor/Company:	Name of Product:	Name of Active Ingredient:
Trevi Therapeutics, Inc.	Nalbuphine Extended-Release	Nalbuphine HCl
	Tablets	

The incidence of adverse events will be summarized through the presentation of proportions by Medical Dictionary for Regulatory Activities (MedDRA) body system classification and preferred term. Vital signs and laboratory data will be summarized using descriptive statistics. The extent and duration of use of prohibited or restricted medications will be similarly summarized using descriptive statistics. No formal statistical analysis will be performed on safety outcomes; inferences, if any, will be derived through clinical review and interpretation.

Adverse events of special interest (AESI) that code to the most relevant abuse-related MedDRA preferred terms will be tabulated and descriptive narratives will be written. Additional adverse events that are considered "possibly related to abuse potential" will be tabulated separately.

Electrocardiograms will be reviewed locally and read centrally by specially trained staff, with real-time feedback to clinical sites regarding any findings relevant to safety. Once the database is complete, ECG data (e.g., heart rate, PR, QTcF intervals) will be presented in listings by subject and summarized by collection date and time. A complete ECG assessment will be documented in a separate report from the central ECG laboratory.

Pharmacokinetics

Nalbuphine (parent and/or metabolites) plasma concentration data will be listed by collection time and nalbuphine dose where applicable. Further PK analyses may be conducted if data allow.

Sample Size and Power

The planned sample size of 44 subjects for the final analysis (22 per sequence) provides at least 80% power to detect a 40% reduction in Day 22 daytime cough frequency (coughs per hour) with NAL ER tablet treatment compared to placebo tablets at the 5% significance level (2-sided). This assumes a coefficient of variation (CV) of 1.00 in log-transformed Day 22 cough frequencies. The CV estimated from *Kelsall et al (2011)* data on chronic cough in patients without esophageal catheterization is 1.12; because Kelsall et al data was on 24-hour cough (including nighttime cough, a period of lower coughing rate) and were not taken in a sample of IPF patients only, it is believed that the CV will be lower than in Kelsall et al data.

If the CV is larger than planned at 1.25, this sample size provides > 80% power to detect a 50% reduction from placebo to NAL ER. Alternatively, if the CV is 0.75, this sample size provides > 80% power to detect a 34% reduction from placebo to NAL ER.

Efficacy analyses will be based primarily on the completers population, which consists of all subjects who received both study treatments and completed both treatment periods in the study. However, methods of adjustment for missing or otherwise incomplete data (e.g., failure to complete both treatment periods) will be considered after assessing the extent that such conditions exist at the time of data base lock.

A total of approximately 60 subjects will be randomized to ensure complete data from at least 44 subjects, assuming up to a potential 26% dropout rate.

A statistical update on this Proof-of-Concept (POC) study may be conducted when a minimum of 12 subjects have completed both study periods for the purposes of determining whether POC can be established prior to complete enrollment of the study.

Date of the Protocol:

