11.1 Sample Size and Power

The planned sample size of 44 subjects for the final analysis (22 per sequence) provides at least 80% power to detect a 40% reduction in Day 22 daytime cough frequency (coughs per hour) with NAL ER tablet treatment compared to placebo tablets at the 5% significance level (2-sided). This assumes a CV of 1.00 in log-transformed Day 22 cough frequencies. The CV estimated from *Kelsall et al (2011)* data on chronic cough in patients without esophageal catheterization is 1.12; because Kelsall et al data was on 24-hour cough (including nighttime cough, a period of lower coughing rate) and were not taken in a sample of IPF patients only, it is believed that the CV will be lower than in Kelsall et al data. If the CV is larger than planned at 1.25, this sample size provides > 80% power to detect a 50% reduction from placebo to NAL ER. Alternatively, if the CV is 0.75, this sample size provides > 80% power to detect a 34% reduction from placebo to NAL ER.

A total of approximately 60 subjects will be randomized to ensure complete data from at least 44 subjects, assuming up to potentially a 26% dropout rate.

A statistical update on this Proof-of-Concept (POC) study may be conducted when a minimum of 12 subjects have completed both study periods for the purposes of determining whether POC can be established prior to complete enrollment of the study.

The analysis will be based on conditional power (CP). Futility will be declared if the CP is < 10%, while efficacy will be declared if the CP > 80% (*Mehta and Pocock, 2010*). If the CP is at least 41%, the number of subjects per treatment arm may be changed to recover the targeted power of 80%. If it is evident that the outcome is influenced by a baseline imbalance in disease characteristics then the baseline imbalance will be taken into account in supplemental analyses.

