4.11.4 Pharmacokinetics

4.11.4.1 Pharmacokinetic Concentrations

Pharmacokinetic plasma concentration of nalbuphine (parent and metabolites), will be listed in Separately set according to SAP section 4.2.4. Listings will include actual sampling times relative to dose administration. Plasma concentrations below the lower limit of quantification (LLOQ) will be presented as Below Limit of Quantification (BLQ) in the listings.

Plasma concentrations of nalbuphine (parent and metabolites) will be summarized by nominal timepoint and as defined in SAP section 4.2.5. The following descriptive statistics will be presented for plasma concentrations obtained at each nominal time point: n, arithmetic mean, SD, coefficient of variation (CV%), geometric mean, geometric CV% (calculated as: $gCV\%=SQRT(e^{s^2}-1)*100$; where s is the standard deviation of the log-transformed values), median, minimum and maximum values.

The following rules will be followed with regards to the number of decimal places and presentation of data in the tables and listings of concentration data:

- Source data shall be used in all derived PK concentrations without prior rounding
- The mean, standard deviation (SD), geometric mean and median will be tabulated to one more significant digit compared to the source data, but with a maximum of four significant digits.
- Minimum and maximum values will be tabulated to the same precision as the source data, but with a maximum of four significant digits.
- Geometric coefficient of variation (CV) % and coefficient of variation (CV%) will be presented to one decimal place.
- 4.11.4.2 Handling of Values Below the Limit of Quantification (BLQ)

All concentrations BLQ or missing data will be labeled as such in the concentration data listings.

Missing samples will be reported as no sample ("NS") and excluded from analysis.

In summary tables, all BLQ values will be set to the ¹/₂*lower limit of quantification (LLOQ), and all descriptive statistics will be calculated.

The number of BLQ values will be reported for each time point

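### The planning CV of 1.00 is attributed to log-transformed cough frequencies, but the stated power reproduces with untransformed within-subject CVs: the scale label is most likely wrong, while 44 completers stands.

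*Protocol*

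**What the plan says.** The protocol synopsis states: "The planned sample size of 44 subjects for the final analysis (22 per sequence) provides at least 80% power to detect a 40% reduction", two-sided at 5%, and gives the variability as "This assumes a coefficient of variation (CV) of 1.00 in log-transformed Day 22 cough frequencies". Protocol 11.1 repeats this ("This assumes a CV of 1.00 in log-transformed Day 22 cough frequencies"), and SAP 4.14 uses the same sentence.

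The protocol adds two scenarios, each with power above 80%: CV 1.25 with a 50% reduction, and CV 0.75 with a 34% reduction. SAP 4.14 has only one: CV 1.25 with a 34% reduction, again above 80%.

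All three places cite a CV of 1.12 from a published chronic-cough study, without giving its scale. No section gives a log-scale SD for cough frequency, a correlation between a subject's two Day 22 values, or a within- or between-subject basis for the CV. The design is a two-period crossover ("This is a double-blind, randomized, placebo-controlled, 2-treatment, 2-period crossover efficacy and safety study in IPF subjects"). The primary analysis is on the natural-log scale (Protocol 11.7, SAP 4.11.2).

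For a different variable, plasma concentration, SAP 4.11.4.1 computes a geometric CV as sqrt(exp(s²) − 1), "where s is the standard deviation of the log-transformed values".

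**The concern.** A CV of logged values is the SD of the logs divided by their mean. Changing coughs per hour to coughs per day shifts the mean log and leaves the SD alone, so this ratio depends on the unit and is not a usable planning input. Two usable readings remain: the SD of the logged values is 1.00, or the CV belongs to the untransformed frequencies. They lead to different power.

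This figure supports the stated 80% and the 44 completers. It is also the benchmark against which the observed variability would be judged, and the primary model reports its variability on the log scale. Someone who took 1.00 as the planned log SD would call an observed within-subject log SD of 0.95 better than planned. If the calculation used 0.83, then 0.95 is worse, and the design would have about 69% power. A crossover also needs the within-subject value, which the sentence does not identify.

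**Working it through.** **Inputs.** From the protocol synopsis and Protocol 11.1: 44 completers, 22 per sequence; two-sided 5%; reductions of 40%, 50% and 34%; CVs of 1.00, 1.25 and 0.75. The between-period correlation ρ is not in the documents; I take 0 and then vary it.

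**Method.** Effect on the log scale = |ln(1 − reduction)|. Standard error = within-subject log SD × sqrt(2/44) = SD × 0.2132. Power comes from the noncentral t with 42 df and noncentrality effect/SE. An untransformed CV converts as SD = sqrt(ln(1 + CV²)).

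**Reproducing the plan's figure.** CV 1.00 gives SD = sqrt(ln 2) = 0.833 and SE = 0.833 × 0.2132 = 0.178. The effect is |ln 0.60| = 0.511 and the ratio 2.88, so power is 80.3%. On this reading 44 is the smallest even number that reaches 80%.

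**All three protocol scenarios.**

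| Figure, reduction | Effect | As untransformed within-subject CV: log SD, ratio, power | As log SD, ρ = 0: ratio, power | As log SD, ρ = 0.31: power |
|---|---|---|---|---|
| 1.00, 40% | 0.511 | 0.833, 2.88, **80.3%** | 2.40, **64.8%** | 80.5% |
| 1.25, 50% | 0.693 | 0.970, 3.35, **90.6%** | 2.60, **71.9%** | 86.4% |
| 0.75, 34% | 0.416 | 0.668, 2.92, **81.3%** | 2.60, **71.9%** | 86.3% |

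In the last column the within-subject SD is the stated figure × sqrt(1 − 0.31). The largest within-subject log SD that gives 80% for a 40% reduction is 0.836. A log SD of 1.00 with ρ = 0 would need 64 completers.

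**Reductions detectable with 80% power.** With untransformed CVs: 39.9% at CV 1.00 and 33.5% at 0.75, close to the stated 40% and 34%. At CV 1.25 it is 44.7%, so the stated 50% is looser but still satisfies the claim.

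**Other readings.**
- If 1.00 is the SD of a subject's difference between periods on the log scale (the same as ρ = 0.5), power is 91.1%. The detectable reductions are then 35.1% at 1.00 and 27.7% at 0.75, well away from those stated.
- If the SD of the logs literally equals their mean, power is about 31% to 10% for assumed median rates of 5 to 30 coughs per hour. These rates are illustrative and are not in the documents.
- If 1.00 is an untransformed CV but a total rather than a within-subject one, power is 80.3% at ρ = 0, 91.9% at ρ = 0.3 and 97.8% at ρ = 0.5. The basis therefore matters on either scale.

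**SAP 4.14 pairing.** CV 1.25 with a 34% reduction: 0.416/(0.970 × 0.2132) = 2.01, power 50.1%.

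**The case against.** The strongest reply is that the stated inequalities do not single out the untransformed reading. Two recordings from the same chronic-cough patient are likely to be correlated, and log SDs of 1.00, 1.25 and 0.75 with a correlation of about 0.31 also meet all three claims. The documents never use the word SD for this figure, and the conversion formula in SAP 4.11.4.1 is for plasma concentrations. This stands: which scale was used is an inference from how closely the numbers fit, and only the original calculation can settle it.

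A reader might go further and infer that the trial was planned with only 65% power, or that 80% can be reached only with an untransformed CV. The documents support neither. The 65% needs a log SD of 1.00 together with zero correlation, and neither is stated.

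The practical consequence is also limited. SAP 4.11.1.4 and 4.11.1.5 record an interim look with no change or re-assessment of sample size, and SAP 4.15 records that recruitment has ended. No section plans a comparison of the observed SD with 1.00.

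What the reply does not rescue is the sentence itself. It gives a quantity that cannot be used as written, and its nearest log-scale reading needs an assumption that appears nowhere.

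**Conclusion.** The basis given for the stated power is wrong or incomplete as written. With no between-period correlation, log-scale SDs of 1.00, 1.25 and 0.75 give 65%, 72% and 72%, against claims of at least 80%. Within-subject CVs of untransformed frequencies meet all three protocol claims, make 44 exactly the number required, and nearly match the stated 40% and 34%. The scale label is therefore most likely the error, and the sample size stands. This rests on a standard 2x2 crossover t-test with 42 df and on the within-subject reading of the CV.

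The single scenario in SAP 4.14 is a separate and plainer fault: on the method that reproduces the protocol, it has about 50% power rather than more than 80%.

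It is tempting to add that the cited CV of 1.12 leaves the design underpowered. That gives about 74% for a 40% reduction if 1.12 is untransformed and within-subject, but the documents state neither, and they explain why a lower CV is expected.

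**What to change.** First check the original calculation. If it used untransformed CVs, replace the sentence in the synopsis, Protocol 11.1 and SAP 4.14 with: *assumes a within-subject CV of 1.00 in untransformed Day 22 daytime cough frequency, i.e. a within-subject SD of 0.83 on the natural-log scale*. In the protocol, add the matching log SDs: 0.97 for CV 1.25 and 0.67 for CV 0.75.

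If the calculation used a log-scale SD of 1.00, state the between-period correlation it assumed, or restate the power as about 65%.

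In SAP 4.14, restore the two scenarios separately: CV 1.25 with a 50% reduction, and CV 0.75 with a 34% reduction. Reporting power at the cited CV of 1.12 is optional, and only with its scale and basis stated.

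The cost is a sentence or two in each of three places, with no new patients, data or analysis. As recruitment is closed, the SAP and the study report are the practical places to carry the correction.
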